### **7.1.3. Maintenance Dosing Period (Period 3)**

The Maintenance Dosing Period (Period 3) will be a double-blind treatment period that will occur from Week 12 (Visit 7) to Week 60 (Visit 19).

In Period 3, safety and efficacy parameters in participating patients will continue to be evaluated according to the Study Schedule ([Attachment 1](#)).

Two treatment groups (80 mg Q4W and placebo) will be evaluated to determine the maintenance of response/remission, the relapse or rebound following treatment withdrawal, and the response to retreatment following relapse (see “Treatment Assignment for Responders” and “Non-responders” below).

Blinded dosing will occur at 4-week intervals throughout Period 3. See Section 9.1 and [Table RHBH.9.1](#) for a full description of all treatment groups. To maintain blinding, each patient will be administered 2 injections of blinded investigational product subcutaneously at Week 12, and each patient will be administered 1 injection of blinded investigational product subcutaneously Q4W from Weeks 16 through 56 (Week 60, no investigational product administration) regardless of his/her assigned treatment group (that is, placebo will be given as necessary to maintain the blind).

At Week 12 (Visit 7), patients who enter Period 3 will be classified as a responder or non-responder according to the following criteria:

- **Responder = sPGA score of “0” or “1”**
- **Non-responder = sPGA score of > 1**

**Treatment Assignment for Responders:** Patients receiving ixekizumab who are responders at Week 12 (Visit 7), will be re-randomized (2:1) to 2 treatment groups (80 mg ixekizumab Q4W or placebo). Patients will be stratified by ixekizumab induction dosing regimen (80 mg Q2W or 80 mg Q4W).

Patients randomized to placebo at Week 0 (Period 2) who are responders at Week 12 (Visit 7) will continue to receive placebo at 4-week intervals during Period 3 until relapse; these patients will receive 2 SC injections of placebo at Week 12 (Visit 7) in order to maintain the study blind.

All treatments will remain in effect until relapse. Relapse (loss of response) is defined as an sPGA score of  $\geq 3$ .

**Treatment Following Relapse:** Patients who are responders at Week 12 will be monitored and assessed for relapse at each visit after re-randomization. Patients who relapse will be treated as follows:

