- Patients receiving 80 mg ixekizumab Q4W, who relapse, will continue on 80 mg ixekizumab Q4W in order to maintain the study blind and to evaluate the long term efficacy of ixekizumab treatment.
- Patients receiving placebo who relapse will be switched to 80 mg ixekizumab Q4W.

Continued treatment for patients who relapse is provided to understand the longer-term efficacy of ixekizumab when treating patients who experience relapse and to maintain study blinding. See Section 8.3.1 for discontinuation criteria.

**Treatment Assignment for Non-Responders:** Patients randomized to ixekizumab at Week 0 (Period 2) who are non-responders at Week 12 (Visit 7) will receive treatment with 80 mg ixekizumab Q4W during Period 3.

Patients randomized to placebo at Week 0 (Period 2) who are non-responders at Week 12 (Visit 7) will receive treatment with 80 mg ixekizumab Q4W during Period 3. These patients will receive a starting dose of 160 mg ixekizumab as 2 SC injections at Week 12 (Visit 7).

Continued treatment for non-responders is provided so that partial or slow responders to ixekizumab and non-responders to placebo may remain in the study and receive treatment with ixekizumab while maintaining the study blind. Some patients may be deriving benefit from treatment with ixekizumab but will be slow responders or partial responders thereby not meeting the “responder” criteria at Week 12. A discontinuation criterion for patients who remain at or above their baseline sPGA score at both Week 12 and Week 24 is included (see Section 8.3.1) to ensure that patients who have not shown any benefit from treatment with ixekizumab can be treated with any other psoriasis therapy as determined appropriate by the investigator.

Once a patient has switched to 80 mg Q4W, regardless of original treatment in Period 2, re-randomization in Period 3, or any assessments of response/relapse, the patient will remain on 80 mg Q4W.

Patients who discontinue the study for any reason during Period 3 will stop treatment and continue to the ETV prior to entering the Post-Treatment Follow-Up Period (Period 4; Section 7.1.4).

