6.1.1. Analysis Population

The following major analysis populations will be used (additional analysis populations for specific analysis will be defined in the corresponding analysis section):

Intent-to-Treat Population (ITT): Unless otherwise specified, efficacy and health outcomes analyses for Period 2 (Induction Dosing Period) will be conducted on the intent-to-treat (ITT) population, defined as all randomized patients, even if the patient does not take the assigned treatment, does not receive the correct treatment, or otherwise does not follow the protocol. Patients will be analyzed according to the treatment to which they are assigned.

Per Protocol Set (PPS): In addition, the primary analysis will be repeated using the per protocol set (PPS), which is defined as all randomized patients who are compliant with therapy, who do not have a subset of important protocol deviations that impact the primary efficacy endpoint (Section 6.5), and whose investigator site does not have significant good clinical practice (GCP) issues that require a report to the regulatory agencies prior to Week 12 (Visit 7). Compliance with therapy is defined to be missing no more than 20% of expected doses, not missing 2 consecutive doses, and no double dosing (that is, taking more injections at the same time point than specified in the protocol) during the period that patients participated in the study and prior to Week 12 (Visit 7) (see Section 6.8). Patients will be analyzed according to the treatment to which they are assigned.

Safety Population: Safety analyses for Period 2 will be conducted on the Safety Population, defined as all randomized patients who received at least 1 dose of study treatment. Patients will be analyzed according to the treatment to which they were assigned.

Maintenance Dosing Period Primary population: defined as all re-randomized patients (that is, patients randomized to ixekizumab in Period 2 who achieved an sPGA (0, 1) and were re-randomized at Week 12) who received at least 1 dose of study treatment during Period 3.

Patients will be analyzed according to the treatment to which they were re-randomized. Only information prior to relapse will be presented.

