Maintenance Dosing Period Secondary population: defined as the ixekizumab patients who were not re-randomized at Week 12 or patients who were randomized to placebo at Week 0, who received at least 1 dose of study treatment during Period 3. Patients will be analyzed according to the treatment to which they were assigned upon entry into Period 3.

Maintenance Dosing Period Relapse population: defined as all patients who were responders at Week 12 (that is, patients who achieved an sPGA (0,1) at Week 12) who first experience a relapse (sPGA ≥ 3) at any point during the maintenance dosing period (that is, Period 3). Although all patients will receive 80 mg Q4W, patients will be analyzed according to the treatment to which they were re-randomized or assigned at Week 12 (see treatment groups defined in [Table RHBH. 6.1.](#)).

Follow-up Population: Safety analyses for Period 4 (Post-Treatment Follow-up Period) will be conducted on the follow-up population, defined as all randomized patients who received at least 1 dose of study treatment and have entered the post-treatment follow-up period. Patients will be analyzed according to the treatment they actually received prior to entering Period 4.

[Table RHBH. 6.1.](#) describes the treatment groups and the comparisons for each study period and the analysis population.

Table RHBH. 6.1. Treatment Groups and Comparisons for Each Study Period and Analysis Population

Study Period	Analysis Population	Treatment Group	Abbreviation	Comparison
Induction Dosing Period (Period 2)	Intent-to-Treat Population; Per Protocol Set; Safety Population	Placebo	PBO	IXE80Q4W vs. PBO; IXE80Q2W vs. PBO; Overall ^a
		Ixekizumab 80 mg Q4W	IXE80Q4W	
		Ixekizumab 80 mg Q2W	IXE80Q2W	
		Total Ixekizumab	Total IXE	
		Total	Total	
Maintenance Dosing Period (Period 3)	Maintenance Dosing Period Primary Population (by Individual Dose)	Ixekizumab 80 mg Q4W/Placebo	IXE80Q4W/PBO	IXE80Q4W/IXE80Q4W vs IXE80Q4W/PBO; IXE80Q2W/IXE80Q4W vs IXE80Q2W/PBO Overall ^a
		Ixekizumab 80 mg Q4W/Ixekizumab 80 mg Q4W	IXE80Q4W/IXE80Q4W	
		Ixekizumab 80 mg Q2W/Placebo	IXE80Q2W/PBO	
		Ixekizumab 80 mg Q2W/ Ixekizumab 80 mg Q4W	IXE80Q2W/IXE80Q4W	
		Total	Total	
	Maintenance Dosing Period Primary Population (by Pooled Dose)	Ixekizumab/Placebo	IXE/PBO	IXE/IXE vs IXE/PBO
		Ixekizumab/Ixekizumab	IXE/IXE	
		Total	Total	
	Maintenance Dosing Period Secondary Population ^b	PlaceboResp/Placebo	PBOResp/PBO	No Comparison
		PlaceboNonR/Ixekizumab 80 mg Q4W	PBONonR/IXE80Q4W	

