		Ixekizumab 80 mg Q4WNonR/Ixekizumab 80 mg Q4W	IXE80Q4WNonR/IXE80Q4W	
		Ixekizumab 80 mg Q2WNonR/Ixekizumab 80 mg Q4W	IXE80Q2WNonR/IXE80Q4W	
		Total Ixekizumab	Total IXE	
	Maintenance Dosing Period Relapse Population	PlaceboResp/Placebo	PBOResp/PBO	No Comparison
		Ixekizumab 80 mg Q4W/Placebo	IXE80Q4W/PBO	
		Ixekizumab 80 mg Q4W/Ixekizumab 80 mg Q4W	IXE80Q4W/IXE80Q4W	
		Ixekizumab 80 mg Q2W/Placebo	IXE80Q2W/PBO	
		Ixekizumab 80 mg Q2W/Ixekizumab 80 mg Q4W	IXE80Q2W/IXE80Q4W	
		Total	Total	
Post-Treatment Follow-Up Period (Period 4) ^c	Follow-Up Population	Placebo	PBO	No Comparison
		Ixekizumab 80 mg Q4W	IXE80Q4W	
		Ixekizumab 80 mg Q2W	IXE80Q2W	
		Total Ixekizumab	Total IXE	
		Total	Total	

Abbreviations: IXE = ixekizumab; Q2W = every 2 weeks; Q4W = every 4 weeks; vs. = versus.

- a Overall comparison will be conducted for demographics, historical illness, medical history, preexisting condition, and previous therapy. The pairwise comparisons and the overall comparison will be conducted for concomitant therapy, compliance, disposition, and safety.
- b For maintenance dosing secondary population, 'Total IXE' is the pooled group of PBONonR/IXE80Q4W, IXE80Q4WNonR/IXE80Q4W and IXE80Q2WNonR/IXE80Q4W.
- c Treatment Group refers to the treatment regimen that the patient received prior to entering Period 4.

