6.1.3. General Considerations for Analyses during Period 3 (Maintenance Dosing Period)

Period 3 starts at the first injection of study treatment at Week 12 (Visit 7) and ends on the date of Week 60 (Visit 19) or the date of the ETV (if it occurs between Weeks 12 and 60).

For Period 3 efficacy and health outcomes analyses, baseline is defined as the last non-missing assessment recorded on or prior to the date of first injection of study treatment at Week 0 (Visit 2). In most cases, this will be the measure recorded at Week 0 (Visit 2).

Unless otherwise specified, for Period 3 safety analyses, baseline and baseline period are defined as the last non-missing assessment prior to the first injection of study treatment at Week 12 (Visit 7). In most cases, this will be the measure recorded at Week 12 (Visit 7). For treatment-emergent adverse events, baseline is the event started prior to the study drug injection at Week 12 (Visit 7) and continued into Period 3.

For patients who met relapse criteria (loss of response; sPGA ≥ 3) and were retreated with ixekizumab, only data up to the time of relapse will be included in the maintenance of effect analyses. These patients will be considered non-responders to categorical assessments per the NRI imputation method (see Section 6.2.1).

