6.12.1.2. Period 3 (Maintenance Dosing Period)

6.12.1.2.1. Maintenance Dosing Period Primary Population and Maintenance Dosing Period Secondary Population

The duration of exposure on maintenance treatment will be calculated as:

$$\begin{aligned} & \textit{Duration of maintenance exposure (days)} \\ &= \textit{Date of last visit (scheduled or unscheduled) or relapse in Period 3} \\ & \quad - \textit{Date of first dose in Period 3} + 1 \end{aligned}$$

Note that patients who experience a relapse during Period 3 will only have their maintenance exposure calculated up until the date of relapse.

The number and percentage of patients in each of the following categories will be summarized: >0 days, ≥7 days, ≥14 days, ≥30 days, ≥60 days, ≥90 days, ≥120 days, ≥183 days, and ≥365 days. Note that patients may be included in more than one category. The number and percentage of patients falling into the following subcategories will also be summarized: >0 to <7 days, ≥7 to <14 days, ≥14 to <30 days, ≥30 to <60 days, ≥60 to <90 days, ≥90 to <120 days, ≥120 to <183 days, ≥183 to <365 days, and ≥365 days.

The summaries will also include the following information:

- Total exposure in patient years, calculated as:

$$\begin{aligned} & \textit{Maintenance exposure in patient years} \\ &= \frac{\textit{Sum of duration of maintenance exposure for all patients in treatment group}}{365.25} \end{aligned}$$

- Mean and median total dose (in mg). For those patients randomized to 80 mg Q4W, the total dose (in mg) taken during Period 3 will be calculated as follows:

$$\begin{aligned} & \textit{Total Period 3 dose} \\ &= \textit{Total number of active injections (including loading doses) received in} \\ & \quad \textit{Period 3 prior to relapse} \times 80 \end{aligned}$$

Note that the total number of injections received will be calculated using the response to the question ‘Was dose administered?’ on the *Exposure as Collected* eCRF page and the actual dose description from IWRS study drug dispense dataset.

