6.12.2. Adverse Events

Adverse events (AEs) will be classified based upon the latest version of the MedDRA. Any condition starting on or after the date of informed consent will be considered an AE. Any preexisting condition which worsens in severity on or after the date of informed consent will be considered and recorded as an AE on the *Adverse Event (AE)* eCRF page from the date of worsening onwards.

A treatment-emergent adverse event (TEAE) is defined as an event that first occurred or worsened in severity after baseline and on or prior to the date of the last visit within the defined treatment period. Both the date/time of the event and the date/time of the dose (that is, injection) are considered when determining TEAEs. Treatment-emergent AEs will be assigned to the study period to which it’s considered treatment-emergent:

- The MedDRA lowest level term (LLT) will be used when classifying AEs as treatment-emergent.
- The maximum severity recorded for each LLT prior to the first dose date/time in the treatment period will be used as the pre-treatment severity for that LLT. If an event during the baseline period has missing severity, and the event persists during the treatment period, then it will be considered as treatment-emergent, regardless of the post-baseline level of severity. Events with a missing severity during the treatment period will be considered treatment-emergent.
- AEs with a particular LLT will be classified as treatment-emergent if they first start on or after the first dose date/time in the treatment period (i.e., a patient has no preexisting conditions with that lowest level term), or if the severity is greater than the pre-treatment severity for that lowest level term. If a partial AE start date/time is present, the date/time

will be compared as far as possible to the treatment start date/time in order to determine whether the event is treatment-emergent or not. If there is any doubt, the event will be flagged as treatment-emergent.

A follow-up emergent adverse event (FEAE) is defined as an event that first occurred or worsened in severity after the date of Visit 19 (that is, Week 60) or the ETV:

- The MedDRA LLT will be used when classifying AEs as follow-up emergent.
- For AEs that are ongoing at the date of Visit 19 or ETV, the maximum severity recorded for each LLT on or prior to the date of Visit 19 or ETV will be used as the follow-up baseline severity for that LLT.

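### In the Secondary Population, safety data collected after relapsing placebo responders switch to ixekizumab stay in the placebo column (PBOResp/PBO), although exposure for that column stops at relapse

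*SAP*

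**What the plan says.** **Treatment.** Under Protocol 7.1.3, placebo patients who respond at Week 12 "will continue to receive placebo at 4-week intervals during Period 3 until relapse". After that, "Patients receiving placebo who relapse will be switched to 80 mg ixekizumab Q4W".

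**Grouping.** These patients belong to the Maintenance Dosing Period Secondary Population. SAP 6.1.1 states: "Patients will be analyzed according to the treatment to which they were assigned upon entry into Period 3". Protocol 12.2.1.3 has the same rule. Table RHBH.6.1 labels them PBOResp/PBO, and footnote b builds Total IXE from the three other groups in this population, so PBOResp/PBO is outside it.

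**Limit at relapse.** The Primary Population definition in SAP 6.1.1 ends with "Only information prior to relapse will be presented". The Secondary Population definition, which follows directly, has no such sentence.

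**Safety window.** SAP 6.1.3 says that Period 3 "ends on the date of Week 60 (Visit 19) or the date of the ETV". SAP 6.12.2 treats as treatment-emergent anything new, and anything that "worsened in severity after baseline and on or prior to the date of the last visit within the defined treatment period". The overall adverse event summary in SAP 6.12.2 names the Secondary Population. The treatment-emergent laboratory and vital-sign summaries (SAP 6.12.4 and 6.12.5) are planned by study period and restrict only the between-group testing to the Primary Population.

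**Exposure.** SAP 6.12.1.2.1, which covers both the Primary and Secondary Populations, says: "Note that patients who experience a relapse during Period 3 will only have their maintenance exposure calculated up until the date of relapse". Total dose there is likewise counted before relapse.

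**The concern.** The rules do not fit together for one group. Once a placebo responder relapses and switches, the patient is on ixekizumab, but the label stays PBOResp/PBO and nothing closes the safety window. The adverse event overview can then list an event on ixekizumab under placebo, while the exposure table for the same column shows no ixekizumab dose for that patient.

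The same event appears a second time in the Relapse Population, again under PBOResp/PBO, although there the SAP does say that everyone receives ixekizumab. It never reaches Total IXE in the Secondary Population.

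What is at stake is the only group still on placebo from Week 0 into maintenance. A reader who uses that column as a long-term placebo safety reference would be looking at a mixture of placebo and ixekizumab time.

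**Working it through.** **1. The plan's own figures.** The documents give no figure for this issue itself. The figures that size it come from SAP 5.3: 420 patients at 2:2:1 give 168, 168 and 84, with assumed Week 12 response of 75% on ixekizumab and 5% on placebo. The stated power above 99% for 168 versus 84 at two-sided 0.025 reproduces (exact Fisher power above 0.9999), so 84 and 5% are the plan's working values.

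**2. Patients affected.** Expected placebo responders = 84 × 0.05 = 4.2, with a binomial 95% range of 1 to 8. If the response rate were 2% or 10%, the expectation would be 1.7 or 8.4. In a column of 4, one patient is 1/4 = 25 percentage points.

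**3. Mislabelled follow-up per patient.** The first scheduled visit after Week 12 is Week 16 (Protocol Attachment 1). Relapse at Week 16 leaves 60 − 16 = 44 weeks; relapse at Week 20 leaves 60 − 20 = 40 weeks. The documents give no relapse timing for placebo responders, so this timing is an assumption.

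**4. How much of the column's safety window is on ixekizumab.** Assume 4.2 patients, all followed to Week 60, a fraction f relapsing, and all relapses at the same week w.

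- Safety window = 4.2 × 48 / 52.18 = 3.86 patient-years.
- Counted exposure = 4.2 × [f × (w − 12) + (1 − f) × 48] / 52.18.
- Share on ixekizumab = f × (60 − w) / 48, which does not depend on the number of responders.

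| Relapse week (assumed) | Exposure counted, f = 50% | Share on ixekizumab | Exposure counted, f = 90% | Share on ixekizumab |
|---|---|---|---|---|
| 16 | 2.09 | 46% | 0.68 | 82% |
| 24 | 2.41 | 38% | 1.26 | 68% |
| 36 | 2.90 | 25% | 2.12 | 45% |
| 48 | 3.38 | 12% | 2.99 | 22% |

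Both f and w are assumptions. The table shows only that the mixture could be slight or could dominate the column.

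**5. Is the cut supplied elsewhere?** The SAP applies a pre-relapse limit in these other places:

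- SAP 6.1.3: maintenance-of-effect analyses and categorical response. This is an efficacy rule.
- SAP 6.4: time to treatment discontinuation, for which the Period 3 population listed is the Primary Population.
- SAP 6.12.1.2.1: exposure and dose, Primary and Secondary Populations.
- SAP 6.13.2.1 and 6.13.2.3: immunogenicity over the combined periods.

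None of these covers adverse events, laboratory values or vital signs in the Secondary Population.

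**The case against.** The strongest reply is that the SAP clearly means to separate time before and after relapse. SAP 6.1.3.3 defines a treatment period that starts at the relapse visit, SAP 6.12 gives relapsers' safety data a relapse baseline, and SAP 6.12.1.2.2 computes retreatment exposure separately. That intention is plausible and explains why exposure is cut. But these passages add a second analysis; none removes post-switch events from the Secondary Population. Read literally, the relapse-baseline sentence also sits awkwardly with the Week 12 safety baseline in SAP 6.1.3.

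It can also be said that grouping by assignment at entry is deliberate and follows the protocol. So it is, but the Primary Population is also grouped by assignment and still has the limit at relapse, and its placebo relapsers switch in the same way.

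The reply on reach stands. Tables by system organ class, preferred term and severity are planned for the Safety and Primary Populations unless noted otherwise, and the common-event, serious-event and discontinuation tables are for those populations too. For the Secondary Population, the affected adverse event output is mainly the overall summary.

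A reader might draw two stronger conclusions that the documents do not support:

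- *That a Week 60 response on ixekizumab would be credited to placebo.* The general Period 3 section (SAP 6.1.3) makes relapsed, retreated patients non-responders for categorical assessments, and SAP 6.1.3.2 applies non-responder imputation to the Secondary Population at every visit, including Week 60. One could argue that the phrase about maintenance of effect means the Primary Population, but the text is not limited to it.
- *That a biased adverse event rate will be reported.* SAP 6.12.2 plans numbers and percentages of patients. The incidence rates mentioned in SAP 6.1.3.2 are not described as exposure-adjusted, and the per-100-patient-year rates in SAP 6.13.2.3 are restricted to information before relapse. The gap between windows would become a wrong rate only if someone divided one table by the other.

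**Conclusion.** The point holds for safety data and is minor. As written, the SAP attributes post-switch safety findings to PBOResp/PBO, omits them from Total IXE, repeats them in the Relapse Population, and closes exposure for the same column earlier than it closes the event window. It looks like a sentence left out rather than a choice.

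About 4 patients are expected, resting on the plan's assumed 5% placebo response; the relapse fraction and timing are unknown. The column is descriptive, Table RHBH.6.1 specifies no comparison for this population, and no primary, major secondary or alpha-controlled result is touched. The events are double-listed rather than lost. It is worth correcting because the column is small enough for one patient to change its appearance and because the correction is cheap.

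**What to change.** Add to the Secondary Population definition in SAP 6.1.1 that, for PBOResp/PBO, only information before relapse is presented, matching the Primary Population. State that safety data after the switch are reported only in the Relapse Population, and relabel that group there so that ixekizumab retreatment is visible. Limit the sentence to PBOResp/PBO: the other three Secondary groups are on ixekizumab from Week 12 and need no cut. While editing, say in SAP 6.12 that the relapse baseline applies to Relapse Population summaries.

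The protocol's grouping rule is unaffected and no new efficacy rule is required. The cost is one or two SAP sentences, one label, and reuse of the relapse date already needed for the Primary Population and for exposure.
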